Arkansas Children's Hospital (ACH) has one of the highest rates of gastroschisis patients in the country and therefore has extensive experience managing these patients. We currently do not know why ACH has one of the highest rates of gastroschisis, but it has been postulated it may be due to some factor more common in low socioeconomic status population. ACH is the only pediatric hospital in the state of Arkansas. Quarterly, reviews of the Children's Hospital National Database (CHND) are performed to track the institutions progress in comparison to national trends. ACH's current surgical practice is to place nearly all patients in a silastic silo for staged reduction. Rarely are patients with gastroschisis treated with primary surgical closure at our institution. Serial reductions are performed and once the abdominal contents are at the level of the fascia the abdomen is closed in the operating room. Previous data indicates an average of five days from birth for final reduction and closure. After closure, there can be significant intestinal dysmotility with a prolonged ileus and a delayed return of bowel function. Generally, those with uncomplicated gastroschisis spend approximately 26 days in the neonatal intensive care unit before discharge home.

From historical CHND data, we know our patients with simple gastroschisis have an average length of stay of 29 days, average of 5 days until abdominal wall closure, average of 7 days until start of enteral feeding after abdominal wall closure and average of 10 days until meeting 100 kcal per kg per day enteral feeds.

Direct Peritoneal Resuscitation

The University of Louisville has been at the forefront of research for Direct Peritoneal Resuscitation (DPR). This technique uses clinically available peritoneal dialysis solution instilled into the abdomen with an initial bolus of 500 mL followed by a rate of 1.5 mL/kg/h in adults undergoing closure of the abdominal wall after traumatic injuries [1].

The aforementioned lab has also studied DPR in a rat model of hemorrhagic shock. The model has shown decreased mortality and increased intestinal and liver blood flow [2-5]. The group further investigated the use of DPR in a rat model of Necrotizing Enterocolitis (NEC) and discovered that 1.5% and 2.5% peritoneal dialysis solutions used as DPR improved intestinal blood flow, and with the 1.5% solution, there was less hyperglycemia than in the group treated with the 2.5% solution [6-10].

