The investigational product will be kept in a secure, limited-access storage in the ACRI research pharmacy under the direction of the research pharmacists who will be responsible for maintaining the supply according to the manufacturer's specifications, dispensing the drug for administration, and maintaining all drug accountability logs.

Study Population

We will prospectively enroll all neonates with the diagnosis of gastroschisis presenting to ACH within 12 hours after birth for whom consent is signed by the parent(s)/LAR. We anticipate enrolling 40 subjects at Arkansas Children's Hospital. All subjects that have their abdominal wall defect closed will be defined as having completed active participation in the study.

Eligibility Criteria

Inclusion criteria:

- Diagnosis of Gastroschisis
- Male or Female, any ethnicity
- Neonates [18]

Exclusion criteria:

- Primary gastroschisis repair
- Vanishing gastroschisis
- Encapsulating peritoneal sclerosis
- Infants < 2 kg and < 34 weeks gestation
- Infants > 12 hours at enrollment
- Severe hypotension, defined as either:
 - Mean arterial blood pressure (MAP) < gestational age in weeks, or
 - Systolic blood pressure (BP) < 45 or diastolic BP < 20
- Severe Hypertension defined as Systolic BP > 90 or diastolic > 60
- Culture-positive sepsis
- Known or strongly suspected inborn errors of metabolism
- Significant cardiac disorders, including cyanotic congenital heart disease, ductal-dependent congenital heart disease, and critical congenital heart disease (lesions requiring surgery or catheter-based intervention in the first year of life)
- Respiratory failure, defined as any requirement of positive pressure ventilation at the time of enrollment, or FiO₂ > 50%

Title: Direct Peritoneal Resuscitation in Gastroschisis

PI: [name]

Sponsor: UAMS

- Any other condition, that, in the opinion of the investigator, might interfere with the safe conduct of the study or place the subject at increased risk
- Lactic acidosis with at least one or more of the following:
 - Characterized by increased blood lactate levels ($> 5 \text{ mmol/L}$) on two occasions at least 6 hours apart
 - Severe metabolic acidosis with an arterial pH ≤ 7.0
 - Bicarbonate < 14 or $\text{CO}_2 < 12$
 - Base excess of $> -10 \text{ mEq/L}$
- Neonatal Acute Renal Failure, defined as serum creatinine $> 2.0 \text{ mg/dL}$ with anuria in the first 12 hours of life
- Neonatal Acute Hepatic Failure, defined as INR ≥ 3 [19]

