We will document the presence of intestinal motility with continuous recording of ultrasound in all four quadrants for 30 seconds. Clips will be stored from each abdominal quadrant with the linear probe. If bowel motility is not recognized by 3 weeks post-operative, then the imaging will be terminated. A separate computer workstation connected to the image server will be used for image viewing and data analysis. Images and videos will be reviewed for quality and assessment of motility. To assess motility, the investigators will identify all distinct bowel loops visualized in the video clips and count movements in each of the bowel loops identified in the clip to determine a motility count for each quadrant. Videos will be classified as poor, fair or good. Motility will be quantified as the total number of distinct peristaltic movements visualized in each abdominal quadrant over 30 seconds. Cumulative motility (CM) will be

Title: Direct Peritoneal Resuscitation in Gastrochisis

PI: [name]

Sponsor: UAMS

calculated as the sum of motility from all four abdominal quadrants. Mean motility (MM) will be calculated as the mean number of distinct peristaltic movements per patient on each day of life imaged. A global descriptive score of bowel activity will also be assigned for each quadrant with the following categories: no, low, normal, or hyperactive peristalsis [20].

Data to be obtained (No. 1-13 are already obtained and available as part of the neonates' medical records):

All data collected as recorded by the NICU for the Children's Hospital Network Database (CHND) will be reviewed for the research. Data with an asterisks () are not included in the standard CHND database.*

1. Demographics
 - a. MRN, admit date, birth date, re-admission, gender, mother's zip code, birth weight, admit weight, gestation, birth head circumference
2. Transport and admission
 - a. Referral source
 - b. Morbidities and diagnoses present at admission
 - c. Lines, tubes, and drains present at admission
3. Maternal, prenatal, perinatal (This is part of the neonates' medical record and will be abstracted from the neonates chart.)

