 - a. Maternal race/ethnicity, age, prenatal care, prenatal vaccination history* (as available) [21], any congenital anomalies that were diagnosed prenatally, maternal substance use history, infant or maternal toxicology screen results, maternal infection history* (including risk factors for infections (as available)) [21], maternal antenatal conditions, antenatal steroids, antenatal magnesium, prenatal ultrasound findings, obstetric antenatal conditions, multiplicity of births, delivery type, APGAR score, indications for C-section
4. Infection
 - a. Blood stream infection, total ventilation days, surgical site infection, and ventilator-associated pneumonia, drain or catheter-related infections
5. Surgery
 - a. Respiratory mode support with surgical time frame, lab values with surgical time frame, complications associated with surgical time frame, surgical procedures, complications
6. Interventions during this admission as recorded by the NICU for the Children's Hospital Network Database
7. Date of discharge from NICU
 - a. Discharge disposition
8. Patients discharge to home/foster care
9. Mortality
10. GI
 - a. Did this infant have functional or structural short gut syndrome at the time of discharge?
 - b. Classification of gastrochisis at time of silo placement - Imaging to be taken at time of initial evaluation.
 - i. Simple
 - ii. Complex: atresia, stenosis, perforation, volvulus
 - iii. Appearance

Title: Direct Peritoneal Resuscitation in Gastroscisis

PI: [name]

Sponsor: UAMS

1. Pristine
2. Matted bowel with peel
3. Staining of amniotic fluid
4. Staining of bowel serosa
- c. # of days of empiric antibiotics
- d. Type/Staging of closure of gastroscisis
- e. Complications associated with closure
- f. Additional closure techniques(s)
- g. Closure timing

11. Other complications

- a. Bacterial overgrowth, late ischemia, NEC, stricture, volvulus, malabsorption, transfer for bowel or liver transplant

12. Feeding and medications

- a. Medications and immunizations [21]
- b. Hyperalimentation
- c. Enteral feedings
 - i. Route of feeding at initiation
 - ii. Reached 100 kcal/kg/d
 - iii. Route of feeding when reached 100 kcal/kg/d
 1. Type of gavage/gastrostomy tube feeding
 - iv. Type of enteral nutrition when reached 100 kcal/kg/d
 - v. Change in feeding regimen
 1. Date change was made
 2. Why change was made

13. Ultrasound

- a. Cumulative motility
- b. Mean motility

14. Additional data

- a. Gastrostomy tube residuals: date, time, and cc

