Demographic variables will be assessed for differences between groups. Categorical variables will be examined using Fisher's Exact Test or Chi Square Test. Continuous data will be examined using Students' T-test. All tests will be two-sided assuming a significance level of 5%. The dependent variable will be tested to ensure the assumption of normality is met.

The primary outcome measure is time to full enteral feeds of 100 kcal/kg/day. Using a two-sample t-test, we estimated that a sample size of 20 in each of the two groups will yield at least 80% power to detect a 6-day difference in mean time to goal enteral feeds (100 kcal/kg/day) assuming a common standard deviation of 7 and a two-sided significance level of 5%.

The proposed data analyses and sample size calculations were conducted with the support of statisticians at ACRI using SAS® Software, Version 9.4[24].

Ethical Considerations

This study is to be conducted according to applicable government regulations and Institutional research policies and procedures.

Title: Direct Peritoneal Resuscitation in Gastroschisis

PI: [name]

Sponsor: UAMS

The parent(s)/LAR of each potential subject identified as meeting inclusion criteria for this study will be approached to discuss participation in this study by trained study personnel. The person obtaining consent will go over the informed consent comprehensively with the parent(s)/LAR. The risks and rationale of this study will be outlined and all questions will be answered. The volunteer natures of this project will be emphasized, including uninhibited withdrawal from the study at any time. No coercion or undue influence will be used in the consent process. A copy of the signed consent will be given to the subject's parent(s)/LAR, and the informed consent process will be documented in each subject's research record in a separate process note.

Ways of consenting parent(s)/LAR:

1. Mother or father (if mother and father are married)/LAR consented prenatally in OB/GYN clinic.
2. Mother or father (if mother and father are married)/LAR consented after birth via faxed consent to the OB unit and returned to PI. The faxed consent will then be witnessed by bedside nurse.
 - a. The person obtaining consent will fax a consent form to the OB unit and conduct the consent process conversation by phone once the mother or father/LAR has the form in hand.

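### The primary comparison is an unadjusted t-test; adjusting for simple/complex class, already recorded at silo placement, may recover some precision, by an amount the documents do not fix

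*Combined protocol and SAP*

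**What the plan says.** **Analysis.** Data Analysis states "Continuous data will be examined using Students' T-test". That sentence follows one on demographic variables, so its use for the primary outcome is partly inferred. The sample-size paragraph supports the inference: it sizes time to full feeds with a two-sample t-test on means, "assuming a common standard deviation of 7 and a two-sided significance level of 5" per cent, with 20 infants per group and a 6-day difference. No covariate-adjusted analysis appears anywhere.

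**Population.** Study Population says "We will prospectively enroll all neonates with the diagnosis of gastroschisis presenting to ACH within 12 hours after birth", subject to consent. Eligibility Criteria exclude primary repair and vanishing gastroschisis, among other conditions, but do not name complex disease. The Randomization section states no stratification factor.

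**The covariate.** The list of data to be obtained, item 10 (GI), includes "Classification of gastrochisis at time of silo placement - Imaging to be taken at time of initial evaluation". Its levels are simple and "Complex: atresia, stenosis, perforation, volvulus".

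**History.** Background and Rationale reports Children's Hospital database averages for simple infants only: "we know our patients with simple gastroschisis have an average length of stay of 29 days", and in the same sentence "average of 10 days until meeting 100 kcal per kg per day enteral feeds". No figure for complex infants is given.

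**The concern.** If complex infants reach full feeds later than simple ones, an unadjusted test puts that difference into the error term, and nothing in the design or the analysis takes it out. The plan gives its history for simple infants only, which suggests that its authors regard class as relevant. Appendix B points the same way: when diet is not tolerated 3 to 4 weeks after closure, a contrast enema is done to look for atresia among other causes, and atresia is one of the features that define complex disease.

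Only precision is at stake. With 40 infants there is little to spare, and a model chosen after the data are seen would be open to challenge, so the choice needs to be made in advance.

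**Working it through.** **1. The plan's own figure.** Inputs from Data Analysis: n = 20 per arm, difference 6, SD 7, two-sided 5%. The standard error is 7 × √(2/20) = 2.214 and the noncentrality is 6 / 2.214 = 2.71. The noncentral t with 38 df gives power 0.752 (normal approximation 0.774). The stated 80% is not reproduced. That is a separate matter, and 0.752 serves here only as the baseline.

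**2. What class adds to the variance.** Let p be the complex share and g the extra days to full feeds in complex infants. Neither is in the documents. If SD 7 holds within each class, the total variance is 49 + p(1−p)g²:
- p = 10%, g = 5: 49 + 2.25 = 51.25, SD 7.16, unadjusted power 0.733
- p = 5%, g = 10: 49 + 4.75 = 53.75, SD 7.33, unadjusted power 0.713
- p = 10%, g = 10: 49 + 9 = 58, SD 7.62, unadjusted power 0.680

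**3. What adjustment does.** Let k₁ and k₂ be the numbers of complex infants in the two arms. The linear model weights the within-class treatment differences by (20−k₁)(20−k₂)/(40−k₁−k₂) for simple infants and k₁k₂/(k₁+k₂) for complex infants. If k₁ or k₂ is zero, the complex weight is zero and the estimate comes from simple infants only. With four complex infants in one arm and none in the other, the simple weight is 16 × 20 / 36 = 8.89. The variance is then 49 / 8.89 = 5.51, against 49 / 10 = 4.90 when two fall in each arm.

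**4. Power by simulation.** 60,000 trials per case (Monte Carlo error about ±0.004), normal errors, the same 6-day effect in both classes, complete outcomes, SD 7 in both classes. The t-test is used when no infant is classed complex. Entries are unadjusted → adjusted.

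| Delay g | 2.5% complex | 5% complex | 10% complex |
|---|---|---|---|
| 3 days | 0.752 → 0.746 | 0.748 → 0.741 | 0.745 → 0.740 |
| 5 days | 0.747 → 0.744 | 0.741 → 0.741 | 0.735 → 0.739 |
| 10 days | 0.732 → 0.744 | 0.714 → 0.741 | 0.679 → 0.741 |

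With no class effect (10% complex), power goes from 0.754 to 0.743. Type I error was 0.045 to 0.051 for both analyses.

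**5. Other assumptions, g = 10, at 2.5%, 5% and 10% complex.**
- Complex infants more variable (SD 14): 0.709 → 0.737, 0.670 → 0.713, 0.598 → 0.657.
- SD 7 already covers both classes together: 0.755 → 0.768, 0.754 → 0.784, 0.753 → 0.826.
- Complex infants missed at initial evaluation (10% complex, equal SD): adjusted power is 0.717, 0.701, 0.687 and 0.680 when 25, 50, 75 and 90% are missed, against 0.679 unadjusted.

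**6. How often the model has anything to adjust.** Let q = (1−p)²⁰ be the chance that an arm of 20 has no complex infant. Then none are enrolled with probability q², and all fall in one arm with probability 2q(1−q).

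| p | q | None in 40 | One arm only |
|---|---|---|---|
| 2.5% | 0.603 | 36% | 48% |
| 5% | 0.358 | 13% | 46% |
| 10% | 0.122 | 1.5% | 21% |

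**The case against.** The strongest case against is that this is a preference between two valid methods. An unadjusted t-test is a legitimate primary analysis of a randomized trial. The documents give no complex share and no delay, and they do not say outright that complex infants feed later. That stands, and it limits the point to an optional improvement.

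Three further objections also stand.
- **The delay matters.** A 10-day delay equals the whole historical average that the plan quotes for simple infants. With equal SDs, a 5-day delay gives almost no gain and a 3-day delay a loss of under one point.
- **Complex infants may be few.** The silo checklist in Appendix B screens for perforation, ischemic bowel and atresia, and the investigator-discretion exclusion could remove others. At low shares the model often reduces to the t-test or takes complex infants out of the treatment contrast.
- **Timing is not free.** Class is recorded at silo placement, and the drain goes in with the silo according to the assigned arm. A class judged then may be judged with the arm known.

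What does not follow is that the point should be dropped. About one point of power is at risk if class is irrelevant, against about 1 to 6 points in the equal-SD cases with a 10-day delay and class correctly recognised.

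**Conclusion.** The point holds in a limited form: the plan leaves a recorded baseline variable out of its primary analysis, and using it **may** recover precision. With SD 7 in both classes, the change in power runs from a loss of about 0.01 (class not prognostic), through essentially nothing (5-day delay), to a gain of about 0.03 (5% complex, 10 days) or 0.06 (10% complex, 10 days). The gain disappears if most complex infants are missed or screened out. Every share and delay is assumed, and the plan does not say whether SD 7 is within class or covers both classes.

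A reader might infer three stronger things, and the documents support none of them.
- **That the t-test is biased or invalid.** It is neither; its type I error stays near 5%.
- **That adjustment is sure to help.** Quoting history for simple infants only, and looking for atresia when feeding fails, hint that class is prognostic. They give no effect size.
- **That adjustment would restore the stated 80% power.** With SD 7 in both classes it only returns power to about 0.74. The shortfall of 0.752 against 80% needs its own answer.

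**What to change.** In Data Analysis, pre-specify the primary analysis as a linear model of time to full feeds on treatment arm and simple/complex class as judged at initial evaluation, with the unadjusted t-test reported alongside. State also that:
- class is recorded before the allocation is revealed and is not changed later, since atresia may be sought weeks after closure;
- if no infant is classed complex, the model reduces to the t-test;
- if all complex infants fall in one arm, the treatment estimate comes from simple infants only.

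**Cost.** A few sentences of text, and about one point of power if class is not prognostic. There is also a procedural cost. Class now sits among the items described as "No. 1-13 are already obtained and available as part of the neonates' medical records". It would need a prospective entry that precedes disclosure of the allocation, inside the 2-hour silo window, which affects the order of examination, randomization and silo placement.

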Hypotheses: We hypothesize that the DPR group will have a more benign hospital course as measured by time to full enteral feeds of 100 kcal/kg/day. We will also assess time to abdominal wall closure, time on TPN, length of hospital stay and intestinal motility post-closure using bedside ultrasounds. Secondly, we hypothesize that there will be no deleterious effects related to introducing the peritoneal dialysis solution into the silo.

Study Objectives

Primary Objectives:

1. To demonstrate that subjects treated with DPR will have a more benign hospital course as measured by time to full enteral feeds. The primary outcome measure will be time to full feeds of 100 kcal/kg/day. Secondary outcomes will include length of time until abdominal wall closure, time on TPN, time to intestinal motility, and total days in the hospital.
2. To demonstrate that the use of DPR in neonates with gastroschisis treated with staged silo closure will result in no significant changes in commonly measured clinical and laboratory safety parameters. This will be measured with more frequent clinical and laboratory assessments for the DPR group. Vital signs and strict intake and output will be monitored every 6 hours for 48 hours after the maximum dialysate infusion volume has been reached, then every 12 hours. Sodium, potassium, blood glucose and lactate levels will be monitored every 6 hours via heelstick, central/arterial line or venipuncture

Title: Direct Peritoneal Resuscitation in Gastroschisis

PI: [name]

Sponsor: UAMS

per NICU standard practice for 24 hours after the maximum dialysate infusion volume has been reached, then every 12 hours through Post-Closure Day 1.

Investigational Product

Dianeal PD-2 1.5% is a sterile, nonpyrogenic, hypertonic peritoneal dialysis solution containing dextrose, a monosaccharide, as the primary osmotic agent. Routine peritoneal dialysis in neonates and infants utilizes up to 40 mL/kg of dialysate per dwell. It will be administered via a 10 mm flat JP drain as a bolus infusion every 6 hours until the abdominal wall is closed (generally 3-5 days), but not to exceed 7 days maximum. The initial bolus infusion will be 10 mL/kg of Dianeal 1.5%. If tolerated, each subsequent infusion will be increased by 10 mL/kg of Dianeal 1.5% up to a goal infusion of 40 mL/kg (to a maximum volume of 100 mL) as tolerated.

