- Liver function test abnormalities defined as AST > 200 , ALT > 200 , GGT > 100 [19]
- Electrolyte abnormalities, defined as:
 - Sodium < 130 or $> 150 \text{ mEq/L}$
 - Potassium < 3.0 or $> 6.5 \text{ mEq/L}$
- Hyperglycemia ($> 150 \text{ mg/dL}$) or hypoglycemia ($< 40 \text{ mg/dL}$)

Note: Potentially eligible subjects may be randomized and the silo placed according to the assigned study arm before all laboratory results are available. Laboratory values will be verified for eligibility prior to administration of DPR. Any ineligible subjects will be withdrawn from the study and may be replaced.

Randomization

The randomization schedule will be generated by the biostatistics department and the Principal Investigator (PI) will maintain a randomization log listing the subjects' ID and study arm assignment. Subjects will be randomized to either the DPR group or SoC group. If the subject is assigned to receive DPR, the ACRI Research Pharmacist will dispense the 1.5% Dianeal solution. The PI will calculate the dose to be distributed based on the subject's weight at the time of enrollment and administer the appropriate volume of 1.5% Dianeal solution as per instructions in the *Investigational Product* section.

Study Design and Procedures

This is a prospective double-arm study designed to evaluate the tolerability of direct peritoneal resuscitation (DPR) in neonates with gastroschisis. The experimental arm (DPR group) will receive adjuvant DPR with standard treatment for gastroschisis (staged silo closure). The control arm (SoC group) will receive standard treatment for gastroschisis only. All subjects will be placed in a silo shortly after birth and within 2 hours of admission to the NICU and subsequently serially reduced in silo with umbilical tape until the bowel contents are at the level of fascia and deemed suitable for closure.

A. SoC Group

[figure not shown]
The SoC group will be placed in silo within 2 hours of admission to the NICU per standard practice. These subjects will have no change in current clinical management by the neonatologists or pediatric surgeons and will not receive peritoneal dialysis fluid.

B. DPR Group

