 - d. Dialysate will dwell for 1 hour after instillation of fluid. Any excess fluid will then be removed via JP drain.
2. Data for DPR
 - a. Blood samples will be obtained at the same time that routine laboratory values are performed. Supplementary research safety labs will require additional blood samples.
 - i. Complete CBC, sodium, potassium, bicarbonate/CO₂, chloride, BUN, creatinine, calcium, phosphate, albumin, glucose and magnesium
 - ii. Labs per standard of care are drawn each morning.
 - iii. Monitoring of additional labs will be per the discretion of the NICU team if necessary for pertinent patient care and monitoring.
 - iv. Heart rate, respiratory rate, blood pressure and pulse oximetry recordings will be recorded as part of the routine patient care. We will collect these measurements every 6 hours (\pm 30 minutes) at the time peritoneal fluid is infused.
 - b. Volume of fluid instillation and removal (date/time) will be documented in the medical record.
 - c. IV Fluids given

Title: Direct Peritoneal Resuscitation in Gastrochisis

PI: [name]

Sponsor: UAMS

Antibiotic regimen for both treatment groups

- 5 days of ampicillin and gentamicin will be given.
- No additional doses beyond 5 days unless clinically indicated.
- Ampicillin Sodium: Q8H, IV (100 mg/kg q8)
- Gentamicin Sulfate: Q24H, IV (4 mg/kg q24)

No additional antibiotics will be given as part of standard care. Post-surgical antibiotics will be administered at the discretion of the surgeon as required.

Standardized treatment algorithms

To minimize inter-subject management variation and bias in the interpretation of the results the following standardized criteria or algorithms are provided:

- i. Timing of abdominal closure/determination of readiness for closure
 - Serial reductions are performed with silastic silo placement for staged reduction using umbilical tape ties. The silo is assessed daily on morning rounds by the surgical team. Once the abdominal contents are at the level of the fascia, the abdomen is closed in the operating room. The average day to closure historically from CHND data is 5 days (Appendix C).
- ii. Initiation and advancement of enteral feeds

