All other standard care laboratory tests will be performed at the discretion of treating neonatologists.

Routine daily labs for gastroscisis patients include:

- Complete Blood Count (CBC) with differential
- Magnesium
- Renal function panel (sodium, potassium, chloride, bicarbonate/CO₂, BUN, creatinine, calcium, phosphate, albumin, glucose)

Research Laboratory Tests

Additional research labs for safety monitoring will be drawn via heelstick, central/arterial line or venipuncture per NICU standard practice. The first capture of research labs should coincide with routine labs to avoid repeat blood draws. Up to 2 mL of blood for research may be drawn each day in addition to the routine daily labs.

SoC Group

A research lab for lactate only will be drawn every 24 hrs (\pm 30 minutes) through Post-Closure Day 1.

DPR Group

Additional research labs will be drawn every 6 hrs (\pm 30 minutes) for 24 hours after the maximum dialysate infusion volume is reached, then every 12 hrs (\pm 30 minutes) through Post-Closure Day 1.

Research labs include:

- Lactate
- Sodium
- Potassium
- Glucose

Glucose via heelstick, central/arterial line or venipuncture per NICU standard practice will also be obtained within 1 hour prior to infusion and 1 hour (\pm 15 minutes) post-infusion for the first day of treatment.

The total amount of blood to be withdrawn per day, accounting for the additional research labs above for safety monitoring, will be up to 3 mL.

Ultrasound

We will perform trans-abdominal ultrasound imaging on all enrolled subjects from the time of abdominal wall closure until feedings have commenced. Additional imaging will be performed if the neonatology team has warranted a stop to feeding the neonate. This noninvasive modality will be used to determine categorization of intestinal motility. Abdominal ultrasound will be performed each morning at the bedside by the PI or other trained study personnel.

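### The plan does not say how serial safety values will be analysed; it should name an analysis that respects repeated measures, uses time points common to both arms and adjusts for the screening value

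*Combined protocol and SAP*

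**What the plan says.** Under Study Objectives, the second primary objective is to demonstrate that DPR "will result in no significant changes in commonly measured clinical and laboratory safety parameters". The supporting data are serial:

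- **Standard of care (SoC) arm.** Research Laboratory Tests: "A research lab for lactate only will be drawn every 24 hrs", continuing through Post-Closure Day 1.
- **DPR arm.** Same section: lactate, sodium, potassium and glucose every 6 hours until 24 hours after the maximum infusion volume, then every 12 hours through Post-Closure Day 1.
- **Routine laboratory tests.** These are daily in both arms; in Set-up for DPR, "Labs per standard of care are drawn each morning".
- **Screening.** The Schedule of Procedures and Assessments lists vital signs, the routine panel and lactate for both groups. The note under Eligibility Criteria has laboratory values verified before DPR is given.

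Data Analysis compares demographic variables between groups, names Fisher's exact or chi-square tests for categorical variables, and continues: "Continuous data will be examined using Students' T-test". It adds a two-sided 5% level, a normality check and the sample size for time to full feeds. Nothing in it mentions repeated values, a time point for testing or baseline.

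**The concern.** A Student's t-test takes one independent value per infant. The safety data supply several correlated values per infant, and the plan does not say how they become one. The sentence therefore allows at least three analyses: a t-test on one value or mean per infant, a t-test at each time point, or a t-test on all values together. Their error rates differ widely, and the choice would be made after the data are in hand. At stake is the evidence for a primary objective: in a pooled analysis, ordinary differences between infants could pass for an effect of DPR in either direction. Separately, a pre-infusion value is already collected in both arms and no analysis uses it.

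**Working it through.** **The plan's own figure.** The documents give no error rate, power or within-infant correlation for the safety data. The only design calculation concerns time to full feeds: a "sample size of 20 in each of the two groups will yield at least 80% power to detect a 6-day difference", "assuming a common standard deviation of 7". Standard error = 7 × √(2/20) = 2.214; 6/2.214 = 2.711; normal-approximation power = Φ(2.711 − 1.960) = 77.4% (75.2% by noncentral t). That falls short of 80%, but it is a separate matter and does not bear on this point.

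**Values per infant, closure on day 5** (the historical mean in Standardized treatment algorithms; follow-up to hour 144).

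- SoC: every 24 h from 0 to 144 h = 7.
- DPR: four infusions 6 h apart reach 40 mL/kg at hour 18 if every step is tolerated, and 18 + 24 = 42. Six-hourly draws from 0 to 42 h = 8; 12-hourly draws from 54 to 138 h = 8; total 16.
- Closure on day 3 gives 5 (SoC) and 12 (DPR); closure on day 7 gives 9 and 20.

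These are laboratory counts. DPR vital signs would number about 18 for closure on day 5. The DPR count also depends on the maximum volume. The schedule defines it as 100 mL, while Investigational Product gives a goal of 40 mL/kg, and an infant under 100/40 = 2.5 kg does not reach 100 mL at that goal. Read literally, the 6-hourly phase would then not end, giving 144/6 + 1 = 25 values. Those passages must be reconciled.

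**Error rate if all values were pooled.** With n infants per arm, m1 and m2 values per infant and exchangeable within-infant correlation r (assumed), the true variance of the difference exceeds the one the t-test uses by

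VR = [(1 + (m1 − 1)r)/m1 + (1 + (m2 − 1)r)/m2] / [1/m1 + 1/m2],

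and type I error = 2 × [1 − Φ(1.96/√VR)]. At r = 0.5:

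- 7 v 7: VR = 1 + 6 × 0.5 = 4.0; 1.96/2 = 0.98; error 33%.
- 7 v 16: VR = (0.571 + 0.531)/0.205 = 5.37; 1.96/2.317 = 0.846; error 40%.

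| r (assumed) | 7 v 7: formula | 7 v 7: simulated | 7 v 16: formula | 7 v 16: simulated |
|---|---|---|---|---|
| 0.2 | 18.6% | 18.9% | 23.7% | 23.8% |
| 0.3 | 24.1% | 23.7% | 30.3% | 30.5% |
| 0.5 | 32.7% | 33.7% | 39.8% | 40.1% |
| 0.7 | 39.0% | 39.4% | 46.3% | 46.5% |

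Simulations used 20 infants per arm and 10,000 null trials per setting. For the same range of r, the formula gives 19 to 39% for 5 v 12 values, 28 to 51% for 9 v 20 and 26 to 49% for 7 v 25. If correlation decays with time instead (24-hour correlation 0.2 to 0.7), 7 v 16 gives 16 to 39%.

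**Error rate with one mean per infant.** Simulated at 4.7 to 5.3% for 7 v 16 values and r from 0 to 0.8. This deals with the correlation. But a raw mean of all values would weight the arms differently over time: 8 of 16 DPR values fall in the first 42 hours, against 2 of 7 SoC values (hours 0 and 24). Any early trend would be mixed with arm, which is why the fix uses common time points.

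**A test at each time point.** Six daily post-screening tests of one analyte would give 1 − 0.95^6 = 26% if they were independent, and less with positive correlation.

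**Baseline.** ANCOVA leaves a fraction 1 − ρ² of the residual variance, where ρ is the correlation of outcome with screening value (assumed). ρ = 0.3 leaves 0.91; ρ = 0.6 leaves 0.64. The reduction is 9 to 36%.

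**The case against.** The strongest reply is that the plan never commits to an invalid analysis. The t-test sentence follows directly on the one about demographic variables, and the normality check speaks of a single dependent variable. One value per infant is a natural reading and keeps the 5% level. A reader might infer from the t-test sentence that all serial values will be pooled, that the false-positive rate is therefore 24 to 47%, and that the safety p-values would be wrong. The documents do not support that. No section says values are pooled, none gives a within-infant correlation, and the 7 v 16 figure also includes the unequal sampling of the arms. With equal daily sampling the range is 19 to 39%, again only under pooling.

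It can also be said that safety will be judged by thresholds: the individual discontinuation criteria, the study stopping rule and the adverse event tables. Counts of infants crossing these are categorical and are covered by Fisher's exact or chi-square tests. That is fair, and no between-arm test of mean laboratory values is spelled out for this objective. But if the t-test sentence does not reach the safety series, those continuous data have no stated analysis, and the same added text is needed.

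Finally, an unadjusted comparison is valid in a randomised trial ("Subjects will be randomized to either the DPR group or SoC group"), so leaving out baseline is not an error. That stands. The gain from adjustment may also be at the lower end, because the eligibility limits on sodium, potassium, glucose and lactate truncate the screening values.

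**Conclusion.** The point holds as a gap in specification. A primary objective relies on serial safety values, and the plan names only a t-test, without saying how each infant's series is reduced or modelled and without using the screening value. One valid reading is available (about 5% error), so it cannot be said that the safety results will be wrong. They could be, if values were pooled: about 19 to 39% type I error with 7 daily values per infant in each arm, and about 24 to 47% with 7 (SoC) v 16 (DPR). These figures rest on closure on day 5, 20 infants per arm, every infusion step tolerated for the count of 16, and assumed exchangeable correlations of 0.2 to 0.7. Baseline adjustment would remove about 9 to 36% of residual variance at assumed correlations of 0.3 to 0.6, possibly less. This is an improvement at almost no cost, not a fatal flaw.

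**What to change.** Add to Data Analysis that each laboratory value and vital sign will be compared between arms using only time points common to both arms, for example the daily routine draw, over a window fixed in advance because follow-up length varies with the day of closure. Then name one of two analyses:

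- one time-averaged value per infant, compared by ANCOVA with the screening value as covariate. This is the simpler choice and suits 20 infants per arm; or
- a mixed model with arm, time, arm-by-time, screening value and a random infant effect.

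Report the adjusted mean difference with its 95% confidence interval for each parameter. The extra DPR samples can still be described within that arm and used for the threshold criteria. The cost is a few lines of text and standard SAS code, with no new data and no additional blood draws.
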